Outcome measures: Venous patency, blood flow direction, peak reflux velocity, circumferences (C1, C2) at the end of each segment length (L), BMI, VRT, Genomic DNA blood test, Estriol (E3) levels, progesterone serum levels, outcome of quality of life.

Population: 70 Random pregnant women.

Eligibility: Pregnant women aged between 18-47 years old.

Duration: 1 year, follow up period will be conducted at the end of first, second and third trimester and three months after giving birth.

1 Introduction

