1.2 Rationale for current study

Regardless of the underlying pathophysiological cause, VV may have a negative social impact on patient's life and negative economic impact on health care budget. VV if left untreated can progress to late stages of chronic venous insufficiency (CVI) which include skin changes and ulceration (Adhikari *et al.*, 2000). Ulcers lower patient's quality of life and may result in social isolation, depression, reduce the ability to work and patients will be dependent on others (Evans *et al.*, 1994; Cesarone *et al.*, 2002). Furthermore, venous disease is costly to manage for healthcare service. For example, the cost of managing chronic wounds caused by ulcers in the UK National Health Service (NHS) during 2005 to 2006 was estimated from 2.3 to 3.1 billion pounds which was equivalent to 3% of total UK health care budget (Posnett, J. and Franks, 2007). Interestingly, the cost was increased between 2012 to 2013 when cost was estimated at 5.3 billions of pounds annually which consume 4% of the total health UK health care budget (Guest *et al.*, 2015).

1.3 Research hypothesis:

The development of post-partum chronic venous insufficiency is predictable and caused by both mechanical and hormonal factors.

2 Study aim and objectives:

The primary aim of this proposed study is to better understand the pathophysiology of VV in pregnant women. This aim will be achieved by meeting the following objectives:

Primary objective:

To develop an antenatal test to predict the risk of developing VV post-partum.

Secondary aims:

1. To evaluate mechanical factors causing VV in pregnancy
2. To evaluate hormonal factors causing VV in pregnancy.
3. To determine whether lower limb pain during pregnancy is related to changes in lower limb venous system.

3 Methods

3.1 Study design:

A prospective longitudinal study will be undertaken to assess the development of VV among pregnant women. This study will follow up patients for one year, starting by following up pregnant women from the first trimester of pregnancy to the end of the second and third trimester. Last follow up will be performed three months after giving birth. Consequently, this proposed prospective study will be conducting four follow ups for each participant.

3.2 Recruiting pregnant women in their first trimester:

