7.2 Study outcome measures

	Intervention/procedure	Outcome measures
Primary outcome	DUS	
 • Patency • Blood flow direction(antegrade/retrograde) • Peak reflux velocity
Secondary outcomes	VFI	
 • Patency • Blood flow direction(antegrade/retrograde) • Peak reflux velocity
	Truncated cone tool	
 • C1 • C2 • h
	PPG	Severity of venous reflux by measuring Venous refiling time (VRT) (Abnormal less than 20 sec)
	Genomic blood test	Genomic DNA
	Hormonal Blood test	Estroil (E3) levels, progesterone serum levels
	AVVQ questionnaire	Outcome of quality of life (0-100). 0 least severe (good quality of life), 100 most severe (low quality of life).

8 Statistics and data analysis

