8.1 Sample size

An exact binomial test with a nominal 5% two-sided significance level will have 91.27% power to detect the difference between the null hypothesis proportion, π_0 of 0.25 and the Alternative proportion, π_1 , of 0.1 when the sample size is **70**.

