8.2 Analysis plan

All analyses will be performed based on the intention of follow-up. The analysis population will include all participants enrolled in the study, including those who developed varicose veins during pregnancy and those who do not.

Analysis of primary and secondary outcomes:

Venous patency and Peak reflux time recordings from VFI scan will be correlated with Venous patency and peak reflux time recordings from DUS scan. This will be performed using descriptive summary statistics. Mixed multivariable logistic regression will be used to model venous patency and peak reflux velocity in each scan.

Secondary outcome which include measuring the circumferences (C1, C2) and length of segments (h) using Truncated cone method. Calculated volume will be determined by summing segment volumes derived from the truncated cone formula. Pearson product moment correlations, paired t tests, and linear regression tests will be used to assess relative association and absolute differences between calculated volumes in each follow up.

Secondary outcome which include PPG will be analysed by comparing the mean value for the venous refilling time (VRT) by Student's *t* test, agreement between DUS and PPG classification was expressed as a kappa (**K**) value.

Genomic DNA blood samples results will be correlated with the UK biobank study. Test statistics will be used to identify genetic variants that influence varicose vein susceptibility.

Each hormonal blood samples results including Estroil (E3) and progesterone serum levels will be correlated with the results of the next follow up to provide comprehensive information about increased hormonal levels in pregnancy and varicose veins development.

Outcome of quality of life statistical analysis will be performed using the Statistical Package for the Social Sciences (SPSS 23.0) for Windows. Evaluation of AVVQ consisted of quality of life in first trimester, second trimester, third trimester and three months after giving birth will be done using the Friedman test.

8.3 Data analysis:

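### The Friedman test named for AVVQ uses only women with all four scores and gives no size of change, although Section 8.2 says all analyses cover all enrolled women

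*Combined protocol and SAP*

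**What the plan says.** Section 8.2 of the combined protocol and SAP opens with a general principle, "All analyses will be performed based on the intention of follow-up", and a population, "The analysis population will include all participants enrolled in the study", whether or not they develop varicose veins (VV).

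The last paragraph of the same section deals with quality of life: "Outcome of quality of life statistical analysis will be performed using the Statistical Package for the Social Sciences (SPSS 23.0) for Windows". It names one method. The evaluation across the three trimesters and "three months after giving birth will be done using the Friedman test".

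AVVQ is a 0-100 score, listed in Section 7.2 as a secondary outcome. It is collected at every visit: Section 3.1 says "this proposed prospective study will be conducting four follow ups for each participant", and the schedule in Section 3.4 agrees. The study summary gives the sample as "70 Random pregnant women".

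The plan foresees incomplete follow-up in several places:

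- Section 3.2 lets women leave at any time without a reason.
- Section 6 withdraws a woman with an incidental finding such as DVT that is likely to have a major impact on her management.
- Section 4.3 excludes incomplete cases such as intrauterine death, and women who fail to attend scans after the first visit.

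The text supplied gives no missing-data rule, imputation method, allowance for dropout or other named AVVQ analysis.

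**The concern.** A Friedman test needs a complete block, here four scores per woman. Run on this study, it describes women who attended throughout pregnancy and again three months after birth. Section 8.2 says the analyses are of everyone enrolled. Nothing in the plan bridges the two.

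Two things are at stake. The first is who the result describes. If missing a visit is related to symptoms, venous findings or pregnancy complications, completers are a selected group. At least one route out of the study, withdrawal after an incidental DVT, follows venous pathology by design. The second is what the result says. The test gives one p value for the hypothesis that scores do not differ across visits. It does not say how far quality of life changed, at which visit, or with what precision.

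**Working it through.** **The plan's own figure.** The only computable figure is in Section 8.1: "An exact binomial test with a nominal 5% two-sided significance level will have 91.27% power", with n = 70, a null proportion of 0.25 and an alternative of 0.10. An equal-tailed exact test rejects if X ≤ 10 or X ≥ 26. Power at 0.10 is 0.9127, so the figure reproduces. It does not concern AVVQ and is not in question.

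**What the test does with a missing score.** In a numerical check on 70 simulated women, 7 lacked the fourth score. With the missing values kept, the test returned no result. With them omitted, it gave exactly the statistic obtained from the 63 complete women alone (0.333, p = 0.954). The other 7 × 3 = 21 scores played no part.

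**Size of the loss.** From the documents: 70 women, four visits. Assumed, because no rate is stated: every woman has a first-trimester score, and a fraction r is lost at each of the three later visits.

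- Women in the test = 70 × (1 − r)³. Scores used = 4 × that number.
- Scores collected under permanent dropout = 70 × [1 + (1 − r) + (1 − r)² + (1 − r)³].
- Scores collected if visits are missed independently = 70 × [1 + 3(1 − r)].

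| r | Women in test | Scores used | Collected, dropout | Unused, dropout | Collected, independent | Unused, independent |
|---|---|---|---|---|---|---|
| 0% | 70 | 280 | 280 | 0 | 280 | 0 |
| 5% | 60.0 | 240.1 | 259.7 | 20 | 269.5 | 29 |
| 10% | 51.0 | 204.1 | 240.7 | 37 | 259.0 | 55 |
| 15% | 43.0 | 172.0 | 223.1 | 51 | 248.5 | 77 |

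The number of women in the test is the same under both patterns. Only the count of unused scores differs, so the pattern has to be stated with the figure.

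A milder case: if 10% or 20% of women each miss exactly one visit, 63 or 56 women remain, and 7 × 3 = 21 or 14 × 3 = 42 collected scores go unused.

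**Interaction with Section 4.3.** The exclusion for failing to attend scans after the first visit can be read as any missed scan or as never returning. Scans and AVVQ fall at the same visits. On the broad reading, largely the same women are removed before any test is run, and a model on all available scores would not include all enrolled women either. On the narrow reading, women with one or two missed visits stay in the study and the Friedman test drops them.

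**The case against.** **The population statement is not a promise about every test.** Section 8.2 says who belongs to the analysis population. It need not mean that each test uses every woman when data are missing. The paired comparisons of limb volume (8.2) and BMI (8.3) also need complete pairs. This stands in part. A reader might infer a flat contradiction peculiar to AVVQ, but the documents support something narrower: a plan-wide gap on missing data, which bites hardest where all four visits are required at once. The sharper textual conflict is between Sections 4.3 and 8.2.

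**The loss is assumed.** This stands. With full attendance nothing is lost.

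**The loss of precision could be overstated.** A reader might compute that, at 10% dropout, the change from first to second trimester would rest on 51 women instead of 63, so that its standard error is √(63/51) = 1.11 times as large. That is the most favourable contrast, and the Friedman test reports no such standard error. Under the same dropout, the change from first trimester to post-partum has 51 observed pairs whichever analysis is used. The 11% should not be quoted as the cost of this test.

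**Comparison by VV status.** A reader might also infer that the plan cannot compare AVVQ between women with and without VV. Section 8.3 provides summaries of continuous variables, and t or Mann-Whitney comparisons by VV at the final trimester. Both are worded by example, so AVVQ could fall under them. No objective in Section 2 asks for quality of life by VV status.

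**A rank test is defensible** for a bounded score that may cluster near zero. This stands, and it is a reason to keep Friedman as a sensitivity analysis.

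**Conclusion.** The point holds in limited form. As written, the one named AVVQ analysis is a completers-only test that estimates no change, in a plan that says its analyses cover all enrolled women and has no missing-data rule. Under an assumed 5% to 15% loss at each later visit, 60 to 43 of 70 women would enter it. Unused scores would number about 20 to 51 under permanent dropout, or 29 to 77 if visits are missed independently. Those counts rest on the assumed rates and on every woman having a first-trimester score. Bias among completers is plausible, but the documents do not allow it to be sized.

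The effect is confined to a secondary outcome. A reader might infer that the study's power is weakened, but the 91.27% rests on a binomial proportion and not on AVVQ. This is a worthwhile improvement, not a threat to the study.

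**What to change.** 1. In Section 8.2, make the main AVVQ analysis a repeated-measures model on all available scores, with visit as a factor and a random intercept for woman. If scores cluster near zero, use an ordinal mixed model, or robust or bootstrap inference.
2. Report change from first trimester to each later visit with a 95% confidence interval.
3. State the missing-at-random assumption, and tabulate the number of scores at each visit with the reasons for missing ones.
4. Keep the Friedman test on completers as a sensitivity analysis.
5. Reconcile the Section 4.3 exclusion of women who fail to attend scans with the all-enrolled population of Section 8.2, and say whether scores already collected from such women are analysed. Without this, the model would not cover all enrolled women either.
6. Treat any comparison by VV status as exploratory, and define when that status is determined (baseline, time-varying or final). Section 8.1 does not say what its proportions describe. If they are VV proportions, 70 × 0.10 = 7 to 70 × 0.25 = 17.5 women would have VV, too few for a visit-by-VV interaction to carry a main conclusion.

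The cost is SAP wording, with no new data. The downside is that the model brings distributional and missing-at-random assumptions, which should be stated. The second may be strained where withdrawal follows a venous finding.

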3.3.4 Protocol for Limb volume assessment

Weight gain during pregnancy is well known. This occurs not only due to fetal growth and uterus enlargement, but also due to water retention and increased blood volume which are required for fetal circulation. This excessive water retention especially in the third trimester is coupled with accumulated fat cause swelling (oedema) especially in both lower limbs. Therefore, measuring limb volume during pregnancy is considered significant to estimate water and fat amounts gained during pregnancy and correlate these findings with potential VV incidence. This proposed study will assess the lower limb volume based on girth measurements using Truncated cone method. This method has the advantage of measuring bilateral limb volume oedema where no comparator (unaffected) limb is available. This method measures limb volume by manual perimetry using tape measure to find limb circumference. Tape measure tension may be inconsistent which can change the limb circumference measurement by up to 3% (Cheah *et al.*, 1989). Therefore, this study will use spring-loaded controlled tension device to keep the tape in closer contact with the skin without compressing the underlying tissue.

Measurements will be taken while the patient is standing. Circumferences will be measured every 10 cm from the sole up to the seventh measurement. A single researcher will measure all patients to prevent differences in tension on the tape. The data will be processed using the truncated-cone formula (Campanholi, Duprat Neto and Fregnani, 2011):

$$V = h (C1 \times C2 + C1^2 + C2^2) / 12\pi$$

V: Volume of each segment (final segment of the limb).

C1 and C2: Circumference measured between the points (at either end of each segment length)

H: Distance between the circles (C1 and C2 in each segment), measured in centimetres.

Total limb volume: is determined by the sum of the segment volumes.

Finally, Patient will be asked to rest and take a seat on a chair, circumferential measurements will be entered into computer software programmes or pre-programmed calculators to calculate limb volume of each recruited patient.

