3.3.7 Protocol for Quality of life assessment

Several quality assessment tools are used to measure the functional impact of a disease on patients' quality of life as perceived by the patient. Both generic and disease specific measures tools are used to estimate patient's quality of life status. This proposed study will use the Aberdeen Varicose Veins Questionnaire (AVVQ) quality of life assessment tool. AVVQ is a disease specific quality of life assessment tool which is developed in specific for patients with VV. Patients will be asked to answer 13 questions which assess patient symptoms such as pain, swelling, itching and ulcers. This tool also assesses the impact of VV on social and daily life activities and the use of support stocking. Perceived cosmetic impact is taken into consideration in AVVQ tool. Each question is designed to reflect the severity of the issue referred to in the question. AVVQ questionnaire is scored from 0-100, where 100 represents the most severe issues related to VV and lowest quality of life while zero represents the best quality of life. Finally, patients will be thanked for their participation and excused.

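### The only AVVQ analysis is one Friedman test over four visits in all women pooled, so it cannot show whether a change in this VV-specific score is related to VV

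*Combined protocol and SAP*

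**What the plan says.** - **Instrument (Section 3.3.7).** The AVVQ was "developed in specific for patients with VV". Its items include pain, swelling, itching, ulcers and support-stocking use. The score runs from 0 to 100, "where 100 represents the most severe issues related to VV". Section 7.2 lists it as a secondary outcome.
- **Who is scored.** Every woman completes it at all four visits (Sections 3.4 and 7). The analysis population in 8.2 is everyone enrolled, "including those who developed varicose veins during pregnancy and those who do not".
- **Analysis (Section 8.2).** The four time points are listed, and the evaluation up to "three months after giving birth will be done using the Friedman test". No other AVVQ analysis is named.
- **Expected pregnancy effect (Section 3.3.4).** "This excessive water retention especially in the third trimester is coupled with accumulated fat cause swelling (oedema) especially in both lower limbs".
- **Nearest related text (Section 8.3).** Continuous variables, with age as the example, are compared by VV status at the final trimester using a t-test or Mann-Whitney test. The AVVQ is not named there, nor among the factors for the longitudinal analysis.

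**The concern.** At least one scored item, swelling, is expected to rise late in pregnancy in women who have no VV. Section 2 also treats the venous origin of leg pain in pregnancy as an open question, so a second scored item has an uncertain source. If the pooled score rises in the third trimester, the planned test cannot separate pregnancy from VV. If VV does worsen quality of life, but only in the women who have it, their change is averaged with that of the others and may be missed. Either way, the study would hold AVVQ and DUS data from every visit without a planned analysis that relates the two over time.

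**Working it through.** **1. The plan's own figure.** The only design calculation is in Section 8.1: an exact binomial test with n = 70, null proportion 0.25, alternative 0.10 and two-sided 5%. Rejection occurs at X ≤ 10 (probability 0.0220 under 0.25) or X ≥ 26 (0.0163). Power is P(X ≤ 10 at 0.10) = 0.9127, which matches the stated 91.27%. It does not concern the AVVQ, and 8.1 does not name the event. If the proportions are VV proportions (an assumption), the VV group is 70 × 0.10 = 7 to 70 × 0.25 = 17.5 women, which leaves 63 to 52.5 without VV.

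**2. What each analysis can see.** Let P be the shift in score at a later visit due to pregnancy, V the extra shift due to VV, and p the proportion with VV.

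- Pooled average movement = P + pV. The Friedman test ranks each woman's four scores and has no grouping term, so it responds to the combined movement and cannot split it.
- With V = 8 and P = 0, the pooled movement is 0.10 × 8 = 0.8 points or 0.25 × 8 = 2.0 points.
- Difference in change, VV minus no VV = V + (P in VV women − P in the others). Pregnancy cancels only if it acts equally in both groups.

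**3. Illustration on assumed inputs.** The documents give no AVVQ mean, SD, item weights or effect. The model takes n = 70, baseline 2 + |N(0, 5)| and within-woman SD 4. The pregnancy shift over the four visits is 0, 0.5d, d, 0, and the VV effect is weighted 0, 0.5, 1, 0.7. The between-group test is Mann-Whitney on change from first to third trimester. Ranges cover repeat runs of 500 to 1,500 simulated studies per setting.

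| Setting | Friedman, p < 0.05 | Change by VV status, p < 0.05 |
|---|---|---|
| No pregnancy rise, no VV effect | about 5% | about 5% |
| Pregnancy rise d = 1, no VV effect | 20-22% | 4-6% |
| d = 2, no VV effect | 70-73% | 4-6% |
| d = 3, no VV effect | 97-98% | 4-6% |
| VV effect 8, d = 0, VV in 10% | 8-9% | 89-93% |
| VV effect 8, d = 0, VV in 25% | 40-45% | over 99% |

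A second model (mean 8, between-woman SD 4, within-woman SD 3, no VV effect) lets only some women have a third-trimester rise. With half of them affected by 2, 4 or 6 points, the Friedman test is significant in 34%, 86% and 99% of studies. The comparison by VV status stays at 4-5%.

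**4. Limits of the comparison by VV status, first model.**

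- With a 4-point VV effect, it detects 38-39% (VV 10%) or 67-70% (VV 25%). With 2 points, it detects about 14% or 22%.
- With no VV effect, a 2-point general rise and 3 points of extra swelling in VV women from other causes, it rejects in about 25-26% or 44-46%.
- If an 8-point VV effect is already present at the first visit and stays constant, change from the first trimester misses it (about 4% rejection).

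**The case against.** The Friedman test is a sound choice for four repeated scores. It is tempting to read the 20-22%, 70-73% and 97-98% above as false-positive rates. They are not: the scores truly rise in those settings, so these figures are power for a real change, and with no rise the test rejects in about 5%. This stands in full.

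A reader might also infer that a significant result will be reported as VV-related loss of quality of life. Section 8.2 states no such attribution, the outcome table in 7.2 describes the score only as good to low quality of life, and no aim in Section 2 concerns quality of life. The VV reading comes from the description of the tool in 3.3.7. So the documents support a gap in what the analysis can show, not a planned misstatement.

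Section 8.3's final-trimester comparison could be stretched to cover the AVVQ, since age is only an example. Even so, it would cover one visit and no change over visits.

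Finally, women without VV might wear support stockings in pregnancy and score for it. The documents do not say that they do. This is an inference from the item list, and the argument rests on swelling alone.

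**Conclusion.** The point holds as a limit on interpretation. The planned test validly describes change over visits but cannot relate that change to VV, and it dilutes an effect confined to women with VV. This follows from Sections 3.3.4, 3.3.7 and 8.2 without any simulation. Its size is not known: the percentages depend on assumed SDs and effects, and on reading the 8.1 proportions as VV proportions.

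A further tempting inference is that comparing change by VV status isolates VV and always keeps a 5% error rate. It does so only if other swelling is equal in the two groups, and Section 3.3.4 itself plans to correlate limb volume with VV. The outcome is secondary and tied to no stated aim, so this is a worthwhile, low-cost improvement and not a threat to the main result.

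**What to change.** In Section 8.2:

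- Keep the Friedman test and the pooled four-visit summary, labelled as a description of leg-symptom burden in pregnancy.
- Add a pre-specified comparison of AVVQ by DUS-defined VV status: a mixed model with visit, VV status and VV-by-visit terms. Report the level difference at each visit, so that VV already present at the first visit is not missed, and the difference in change from the first trimester, each with a 95% confidence interval. State the DUS definition of VV and whether a woman's status is updated at each visit.
- Add a sensitivity analysis that drops the swelling and stocking items or adjusts for limb volume, because swelling may differ by VV status. It should stay a sensitivity analysis: if VV itself causes swelling, either step removes part of a true effect.

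In Section 3.3.7, state that scores in women without VV are not read as VV severity.

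The cost is wording and a modest amount of analysis. AVVQ, DUS and limb volume are already taken at all four visits, and dropping items only requires that item responses are kept. The VV group is probably small (about 7 to 18 women on the assumption above), so intervals will be wide, and the comparison is observational, so confounding will remain.

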The data obtained will be subjected to statistical analysis by an independent biostatistician. SPSS Version 23.0 or/ and STATA Version 10.0 will be used for statistical analysis. Measures such as the mean and standard deviation or median and interquartile range will be used to summarise continuous variables such as age and BMI. Tables reporting the numbers and percentages will be used for categorical variables such as varicose veins and smoking. Chi square or Fisher's exact test will be used to compare categorical variables such as varicose veins and smoking at the final trimester. The t-test or Mann-Whitney test will be used to compare continuous variables such as age with varicose veins at the final trimester. The paired t-test or Wilcoxon signed-rank test will be used to compare BMI between first and third trimester. The Kappa statistic will be used to compare DUS and VFI regarding direction and velocity. Longitudinal analysis will be used to look at factors associated with varicose veins. Factors include age, BMI, smoking, ethnicity, pregnancies and family history. A significance value (p-value) less than 0.05 is considered statistically significant.

9 Regulatory issues

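### The primary objective is to predict varicose veins after birth, but no planned analysis takes post-partum varicose veins as its outcome or measures prediction, and the two explicit group comparisons are fixed at the final trimester.

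*Combined protocol and SAP*

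**What the plan says.** The primary objective in section 2 is: "To develop an antenatal test to predict the risk of developing VV post-partum". The hypothesis in 1.3 also looks beyond delivery: "The development of post-partum chronic venous insufficiency is predictable and caused by both mechanical and hormonal factors". Sections 3.4 and 7 repeat DUS and the other assessments at a fourth visit three months after birth, so the outcome data will exist.

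Section 8.3 specifies two between-group tests involving VV. The chi-square or Fisher test is "used to compare categorical variables such as varicose veins and smoking at the final trimester". The t or Mann-Whitney test will "compare continuous variables such as age with varicose veins at the final trimester". The variables are examples; the time point is not. Section 8.3 adds: "Longitudinal analysis will be used to look at factors associated with varicose veins". It continues: "Factors include age, BMI, smoking, ethnicity, pregnancies and family history".

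Section 8.2 states: "Mixed multivariable logistic regression will be used to model venous patency and peak reflux velocity in each scan". It also plans to correlate each hormone result with the following visit, to test genetic variants for VV susceptibility, and to compare venous refilling time (VRT) by t test. Elsewhere, 3.3.4 (limb volume), 3.3.6 (progesterone and estriol), 3.2 (fetal weight) and 13.1 (pregnancy complications) each state an intention to correlate the measure with VV or venous pathology.

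The primary outcome in 7.2 is DUS patency, flow direction and peak reflux velocity. It gives neither VV status nor a visit.

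**The concern.** A predictive objective needs an outcome observed at the stated time and a measure of how well the predictor performs. The plan commits to neither. Its two fully timed VV comparisons take place before the post-partum outcome can be seen. They serve the secondary aims on VV in pregnancy, which is a different question from the primary one.

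The study could therefore finish with complete data and no pre-planned result on its main objective. The case definition, visit, predictors and performance measure would then be chosen with the data from 70 women already in hand, which invites selective reporting.

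**Working it through.** **1. Objective against analyses.** Each planned analysis that touches VV or venous pathology is set against two requirements: post-partum VV named as outcome, and predictive performance measured.

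| Analysis | Time point | Post-partum VV named as outcome? | Performance measure? |
|---|---|---|---|
| Chi-square/Fisher (8.3) | Final trimester | No | No |
| t/Mann-Whitney (8.3) | Final trimester | No | No |
| Longitudinal analysis (8.3) | Not stated | No | No |
| Mixed logistic model (8.2) | Each scan, which may mean each visit or DUS and VFI | No; patency and reflux velocity | No |
| Hormone correlation (8.2) | Next visit; post-partum for the third-trimester sample | No; VV development is only a general purpose | No |
| VRT t test (8.2) | Not stated | No; groups not stated | No |
| Genetic variants (8.2) | Not stated | No; VV susceptibility | No |
| Limb volume (3.3.4), hormones (3.3.6), fetal weight (3.2), complications (13.1) | Time of VV not stated | No | No |

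The rest of 8.2 and 8.3 compares limb volume, BMI or quality of life between visits, or assesses DUS against VFI or PPG. The only analysis there that names the post-partum visit is the Friedman test on AVVQ, a quality-of-life score. No sensitivity, specificity, AUC, cut-off or calibration appears in either section.

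**2. Whether the sample size fills the gap.** Inputs from 8.1: n = 70, null proportion 0.25, alternative 0.10, two-sided 5%. With 2.5% per tail, the exact binomial test rejects if X ≤ 10 (tail probability 0.0220) or X ≥ 26 (0.0163). Power at 0.10 is 0.9127, which reproduces the stated 91.27%. This is the power to test one proportion that 8.1 does not identify. It says nothing about prediction.

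**3. Precision of the missing analysis.** The documents give no post-partum VV rate. Borrowing the two proportions in 8.1 as an assumed range gives 70 × 0.10 = 7 cases and 70 × 0.25 = 17.5, taken as 18. For an assumed AUC A = 0.75, the Hanley-McNeil variance is

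[A(1−A) + (n1−1)(q1−A²) + (n2−1)(q2−A²)] / (n1·n2),

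with q1 = A/(2−A) = 0.6000, q2 = 2A²/(1+A) = 0.6429 and A² = 0.5625.

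- 18 cases, 52 non-cases: (0.1875 + 17 × 0.0375 + 51 × 0.0804)/936 = 0.00526; SE 0.0725; 95% CI 0.61 to 0.89.
- 7 cases, 63 non-cases: (0.1875 + 6 × 0.0375 + 62 × 0.0804)/441 = 0.01223; SE 0.1106; 95% CI 0.53 to 0.97.

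**4. What final-trimester VV could do as a stand-in (illustration only).** Let r be the share of final-trimester VV that resolves by three months. The documents give no value, so r is set at 0, 0.25 and 0.5, and no VV is assumed to arise first after birth.

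- A measure with AUC 0.75 for persisting VV and no relation to VV that resolves shows 0.75(1−r) + 0.5r = 0.75, 0.69 and 0.63 at the final trimester.
- A measure related only to VV that resolves, at r = 0.5, shows 0.75 × 0.5 + 0.5 × 0.5 = 0.63 at the final trimester. Against post-partum VV it shows (63 × 0.5 + 3.5 × 0.25)/66.5 = 0.49 with 7 final-trimester cases, or (52 × 0.5 + 9 × 0.25)/61 = 0.46 with 18.

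The error can run either way, and it is zero if nothing resolves.

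**The case against.** The strongest reply is that the plan does more than two final-trimester tests. Limb volume, hormones, fetal weight and complications are all meant to be correlated with VV or venous pathology. The longitudinal analysis could include the last visit, and its factor list need not be exhaustive. For the third-trimester hormone sample, the next visit is the post-partum one, so that correlation does run from an antenatal measure to a post-partum result. All of this stands. A reader might infer that the plan ignores post-partum data, or never relates mechanical and hormonal measures to VV. The documents do not support either reading. What remains is that none of these analyses names post-partum VV as its outcome, and that association or correlation does not show how well a test performs.

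A second reply is that the final-trimester tests are legitimate. That also stands: they fit the secondary aims, and the defect is the missing primary analysis.

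A third is that the AUC scenarios are hypothetical. They are. The fall from 0.75 to 0.63 lies inside both confidence intervals above, so the proposed analysis could not reliably tell those two values apart. The scenarios cannot carry the point, and it does not rest on them.

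**Conclusion.** The point holds as a mismatch between objective and analysis. Followed as written, the plan yields VV comparisons in late pregnancy and no result on how well any antenatal measure predicts VV three months after birth. This rests on sections 2, 7.2, 8.2 and 8.3 alone and needs no assumption. It should be corrected before analysis, because it concerns the primary objective.

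A reader might go further and infer that using final-trimester VV would bias the answer by a known amount. The documents do not support that: they give no resolution rate, and the illustration assumes that no VV first appears after birth. The case numbers and the AUC of 0.75 are also assumptions, used only to show the likely precision.

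**What to change.** - **Outcome.** In 8.3, make VV at the three-month post-partum DUS the outcome of the main VV analysis, one outcome per woman, and list it as the primary outcome in 7.2. State an explicit DUS case definition. Section 3.3.2 defines incompetence by reflux over 0.5 seconds but does not equate that with VV.
- **Final-trimester tests.** Keep them as secondary.
- **Prediction.** Relate a short pre-specified list of antenatal measures already collected, from a stated antenatal visit, to that outcome. Report discrimination, for example AUC, with 95% CIs, and label the analysis exploratory. The choice of measures and visit is the sponsor's.
- **Disease at entry.** The exclusions in 4.3 do not list existing VV. Report women with VV or reflux at the first-trimester DUS separately from those who develop it later. That visit is set at the end of the trimester in 4.4 but at any time from 0 to 13 weeks in 3.4. Say that VV arising before it counts as present at entry; 1.1 notes that VV may begin in that trimester.

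**Cost.** Wording in 7.2 and 8.3 and modest analysis work, with no new visits or samples. The drawback is few cases and wide intervals, wider still after losses or after separating entry disease. The plan should also say that the 91.27% power in 8.1 does not apply to this analysis.
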